## **1. Introduction**

Sleep plays a crucial role in a child's development, contributing to cognitive functioning, emotional stability, recovery and overall wellness (Baddam & Nasser, 2021; Blackwell et al., 2020). Prolonged and intensive treatments received by paediatric oncology patients can lead to sleep disturbances that many carers and healthcare professionals overlook as transient side effects (Daniel et al., 2019). Sleep disturbances can be presented as a cluster of symptoms including difficulty initiating or maintaining sleep, reduced sleep duration, or perceived poor sleep quality (Richards & Pao, 2014). Recent studies showed that prevalence rates of sleep disturbance in leukemia survivors range from 13% to 50% (Russell et al., 2020), and up to 80% in children with central nervous system tumours (Rosen & Brand, 2020). Furthermore, a recent Hong Kong study by Ho et al. (2022) revealed that around 45% of pediatric oncology survivors struggle with ongoing sleep, which highlights the relevance of this issue globally as well as in local areas.

Sleep disturbances in this vulnerable population stem from factors such as pain and nausea from side effects of chemotherapies, and corticosteroids exacerbate these disturbances (Gedaly-Duff et al., 2006; Hinds et al., 2007; Lee et al., 2017). Not only would sleep disturbances cause immediate discomfort, but it would also significantly impact paediatric oncology patients' treatment adherence, daily activities, social engagement and quality of life (Cheung et al., 2017; Matricciani et al., 2019).

While pharmacological approach remains to be the go-to management for paediatric sleep disturbances, with about 60% of paediatric oncology patients being prescribed with sedatives (Walter et al., 2015), this approach carries extensive risks. Polypharmacy can lead dangerous drug interactions and development of drug dependency (Dhir et al., 2024; Owens et al., 2010). In contrast, non-pharmacological options allow patients and caregivers to manage their sleeping problems without increasing medication burden (Rogers et al., 2019), and also encourage patients and families to take a more proactive

role in managing patients' sleep health.

The Dreamcatchers Programme was developed as a nurse-led initiative in response to the pressing need of improving sleep quality in pediatric oncology patients. The programme supports relaxation and offers sustainable strategies for better sleep by introducing sleep hygiene, progressive muscle relaxation (PMR) and breathing control exercises to patients and carers. Evidence-based intervention supplies nurses with techniques built on holistic care, bridging gaps in nursing knowledge and skills.

This project proposal outlines a randomized controlled pilot study to evaluate the feasibility and preliminary effectiveness of the Dreamcatchers Programme, laying the foundation for a standardized sleep management protocol in pediatric oncology care. The following sections detail the literature base, service gaps, study design, and implementation strategies supporting this initiative.

## **2. Literature Review**

A systematic review of non-pharmacological interventions for sleep in pediatric oncology was conducted from December 2023 to April 2024, with an extended search period through March 2025. The review analyzed the results of nine studies that implemented various strategies like music therapy, cognitive-behavioral interventions, physical activity and mindfulness (Hinds et al., 2007; Jacobs et al., 2016; Khoirunnisa et al., 2019; Liu et al., 2019; Rogers et al., 2019; Sriasih et al., 2019; Sulistyawati et al., 2021; Tanriverdi et al., 2022; Zupanec et al., 2017). Databases such as MEDLINE (Ovid), EMBASE (Ovid), PsycINFO, CINAHL and Cochrane Library were used in this review and the articles searched for non-pharmacological solutions to sleep problems. These interventions align with Spielman's behavioral model of insomnia, addressing the factors that contribute to, exacerbate, or maintain sleep disturbances (Spielman et al., 1987).

The systematic review identified interventions that promote relaxation through physiological and psychological mechanisms and summarized in Appendix I. The interventions included in the 9 studies induce relaxation by reducing hyperactivity, muscle tension, and anxiety, which typically affect sleep in pediatric oncology patients. Practicing breathing exercises like diaphragmatic breathing can stimulate the

parasympathetic system, leading to a reduction in heart rate, cortisol level, and feelings of arousal which supports sleep at night (Chen et al., 2016; Murphy, 2019). Doing gentle routines while focusing on muscles helps ease tension in the body, lessen discomfort caused by treatment and encourage relaxation for better sleep (Khoirunnisa et al., 2019; Sulistyawati et al., 2021). Sleep hygiene education is a central part of cognitive-behavioral approaches and supports establishing good sleep routines and a suitable sleep environment, which minimizes factors that can disrupt sleep (Rogers et al., 2019; Sriasih et al., 2019; Zupanec et al., 2017).

Mindfulness and education-based multicomponent approaches have been shown to reduce stress and help improve sleep quality (Liu et al., 2019; Sriasih et al., 2019). Zupanec et al. (2017) found that having a four-week relaxation and education program boosted sleep duration, underlining the efficacy of multicomponent approaches. Complementary therapies like massage showed subjective improvements in sleep and fatigue, yet quantitative outcomes were less robust (Jacobs et al., 2016). Physical activities including virtual reality-based exercises yielded mixed results, suggesting integration of physical activity with relaxation techniques would be more impactful (Tanrıverdi et al., 2022). Nonetheless, the review demonstrated the feasibility of nurse-led delivery and highlighted the need for well-outlined steps.

## **2.1 Theoretical Framework**

Spielman's model provides a framework for understanding how relaxation-based interventions address sleep disturbances by targeting predisposing, precipitating, and perpetuating factors (Spielman et al., 1987): Pediatric oncology patients are predisposed to insomnia due to baseline anxiety and stress from their diagnosis and treatments. Breathing and PMR exercises counter hyperarousal by engaging the parasympathetic nervous system, reducing cortisol levels and anxiety, enabling easier relaxation and sleep onset (Annisa et al., 2018; Chen et al., 2016). Regular practice mitigates cancer-related stress, addressing predisposing vulnerabilities (Sulistyawati et al., 2021).

Treatment-related pain, nausea, and emotional distress from hospitalization are categorized as precipitating factors that can trigger insomnia. Breathing and PMR exercises alleviate physical discomfort by releasing muscle tension and diverting

attention from pain, reducing the impact of precipitating factors (Khoirunnisa et al., 2019; Sulistyawati et al., 2021). These techniques are accessible and require minimal equipment, unlike music therapy, which may rely on trained professionals or resources (da Silva Santa et al., 2021; Ramanda et al., 2022).

Frequent naps or irregular sleeping times can decrease sleep drive which perpetuates to further sleep disturbances. Promoting regular routines and a suitable sleeping environment through education with caregivers can change these patterns (Rogers et al., 2019; Zupanec et al., 2017). Moreover, breathing exercises calm children and help them get back to sleep in case of nighttime awakenings (Murphy, 2019).

Breathing and PMR exercises offer distinct advantages over other interventions like music therapy or mindfulness. These techniques are simple, requiring no specialized equipment or extensive training, making them suitable for hospital or home settings (Chen et al., 2016). They can be adapted into playful activities (e.g. imagining squeezing lemons), engaging younger children who may struggle with mindfulness due to limited cognitive maturity (Burke, 2010; Burrows, 2022). Breathing and PMR exercises are cost-effective and scalable (da Silva Santa et al., 2021). They can alleviate physical discomforts to facilitate relaxation and enhance sleep as opposed to mindfulness that primarily targets mental and emotional dimensions (Sulistyawati et al., 2021).

## **2.2 Literature Gaps**

Despite promising findings from the systematic review, standard procedures for managing sleep in children with cancer are found to be lacking in the published literature. Most of the measures taken were brief and there was no data available for long-term evaluation. The existing studies rarely review the sleep differences among children of various ages or the ways caregivers assist with sleep routines. Methodological limitations, including small sample sizes, reliance on self-report measures, and inconsistent reporting of intervention fidelity result in poor reproducibility.

## **3. Service Gaps**

Sleep disturbances among paediatric oncology patients are often thought of as

temporary, instead of requiring more specific care (Daniel et al., 2019). Patients seldom report their sleep issues thus the problem is rarely being assessed. In current Hong Kong's clinical practice, there are no standardized protocols for addressing sleep disturbances, and bundled care approaches are often hindered by intensive treatments in minimizing patients' sleep disturbances. Zhou and Recklitis (2014) reported that nearly two-thirds of pediatric oncology patients did not get a routine check of their sleep-related issues during long-term follow-ups. This oversight results in a passive approach to addressing sleep complaints, only addressing them when they severely disrupt daily functioning. Consequently, cancer children experience sleep deprivation which can worsen their exhaustion, mood and performance.

While standardized non-pharmacological techniques are lacking, most sleep problems in children with cancer are managed with drugs, with over half of these patients prescribed with sedatives (Walter et al., 2015). Nevertheless, children who take multiple drugs and are given sedatives may face increased risks such as of addiction, mental fog and potential negative interactions between drugs (Dhir et al., 2024; Owens et al., in 2010), causing extra burden on caregivers, thus proving that new safe options are necessary.

Hong Kong nurses in paediatric oncology lack special training in sleep assessments and behavioral interventions. The integration of sleep care into holistic nursing practice relies on the development of guidelines and institutional support. Although there is evidence for non-pharmacological interventions, they face challenges due to lack of proper training for staff and practical logistical issues in hospitals.

#### **4. Study Objectives**

The Dreamcatchers Programme aims to close the gap by using a well-structured and evidence-based method developed by nurses for Hong Kong paediatric oncology patients. The pilot study seeks to evaluate the feasibility and preliminary efficacy of a nurse-led, non-pharmacological intervention designed to improve sleep quality in pediatric oncology patients. Grounded in behavioral approaches and integrated into routine clinical practice, the programme combines sleep hygiene education, PMR, and breathing control techniques. The specific objectives of this pilot study are as follow:

1. Primary Objective:

To improve sleep quality (perceived restfulness), sleep latency, habitual sleep efficiency, sleep disturbances and duration in pediatric oncology patients aged 6–12 years, as measured through Chinese version of the Pittsburgh Sleep Quality Index (PSQI).

2. Secondary Objective:

To enhance the overall quality of life of participating children by promoting better sleep patterns during active cancer treatment and assess through Chinese version of Pediatrics Quality of Life Inventory (PedsQL) 3.0 Cancer Module.

3. Feasibility and Acceptability Objective:

To assess the feasibility of the study, the recruitment, response, and retention rates will be documented. To assess the acceptability of the intervention by healthcare professionals and participants, a satisfaction survey and process evaluation will be conducted. The process evaluation is to assess whether the intervention is delivered as planned and to identify patients' perspectives on the intervention's strengths and limitations. The findings should help improve the effectiveness of the intervention and show if both healthcare workers and participants find the intervention usable and acceptable.

These objectives reflect a commitment to advancing holistic, evidence-informed strategies within pediatric oncology settings, with the long-term aim of strengthening nurses and ensuring better outcomes for patients, turning sleep management into a regular care plan for pediatric oncology.

## 5. Hypothesis

The Dreamcatchers Programme pilot study hypothesizes that:

1. Primary Hypothesis:

The nurse-led multicomponent intervention will significantly improve sleep quality in pediatric oncology patients aged 6–12 compared to the waitlist control group, as measured by the Chinese PSQI, enhancing perceived restfulness, sleep latency, habitual sleep efficiency, sleep disturbances, and duration at T1 and T2.

## 2. Secondary Hypothesis:

The intervention will enhance quality of life in patients undergoing active cancer treatment compared to the control group, as assessed by the Chinese PedsQL Cancer Module 3.0 at T1 and T2.

## 3. Feasibility and Acceptability Hypothesis:

The intervention will be feasible (measured by recruitment, response, and retention rates) and acceptable to participants and healthcare professionals (evaluated via satisfaction surveys and semi-structured interviews), supporting integration into routine clinical practice.

## 6. Outcome Measures

The primary outcome focuses on improvements in sleep quality among pediatric oncology patients aged 6–12 years, as measured by the Chinese version of the Pittsburgh Sleep Quality Index (PSQI). Specifically, the study aims to assess:

- Perceived restfulness: Subjective sense of feeling rested after sleep.
- Sleep latency: Time taken to fall asleep.
- Habitual sleep efficiency: Ratio of total sleep time to time spent in bed.
- Sleep disturbances: Frequency and severity of disruptions during sleep.
- Sleep duration: Total amount of sleep obtained per night.

These components are captured through the PSQI global score, where a lower score indicates better sleep quality.

The secondary outcome focuses on enhancing the overall quality of life of participating children during active cancer treatment, as measured by the Chinese version of the Pediatric Quality of Life Inventory (PedsQL) Cancer Module 3.0. This includes:

- Health-related quality of life: Assessed through subscales addressing pain, fatigue, cognitive problems, and other treatment-related symptoms.

Higher PedsQL scores indicate better quality of life.

Additionally, the study evaluates feasibility and acceptability as secondary outcomes to determine the intervention's potential for integration into clinical practice:

- Feasibility: Measured by recruitment rates, response rates, and retention rates throughout the study.
- Acceptability: Assessed through a custom-designed satisfaction survey (with Likert-scale and open-ended questions) and semi-structured interviews conducted with the intervention group at T1.

These tools evaluate the clarity of educational materials, ease of performing exercises, perceived benefits, and overall satisfaction with the Dreamcatchers Programme.

## 7. Study Design

This study is structured as a pilot prospective and randomized controlled trial (RCT) with a 1:1 allocation to either the intervention group or waitlist control group. The intervention group will receive the Dreamcatchers Programme, including sleep hygiene education, PMR, and breathing control exercises, which will be delivered over 4 weeks with weekly in-person follow-ups. The waitlist control group will continue to receive routine hospital support and pediatric oncology health information (e.g., neutropenic diet tips) to maintain engagement without sleep-specific strategies. The trial will span 4 weeks, followed by a 3-month follow-up to assess the sustainability of outcomes.

### 7.1 Randomization and Allocation

The study will arrange participants in intervention and waitlist control groups at a 1:1 ratio through block randomization. A computer will be used to generate blocks for randomization to guarantee all the groups are of equal size and to minimize the risk of allocation bias. The randomization sequence is kept secret in sealed but opaque envelopes and will not be opened until enrollment, therefore lowering the chances of selection bias.

### 7.2 Blinding Procedures

Given the nature of the intervention, blinding participants and caregivers would not be feasible. However, outcome assessors, especially the nurses responsible for data collection, will remain unaware of group assignments. This single-blind design aims to reduce observer bias during data recording and interpretation.

### **7.3 Contamination Prevention**

To prevent contamination, sessions for the intervention group will take place in a separate location (e.g., an educational room away from clinical areas) distinct from control group activities. Access to QR code videos will be password-protected for the intervention group, ensuring that control participants do not receive any intervention materials.

### **7.4 Duration**

The intervention will last for 4 weeks, with data collection points at baseline (T0), immediately post-intervention (T1), and 3 months post-intervention (T2) to evaluate both short-term and sustained effects.

## **8. Sampling Method and Sample Size Planning**

A simple random sampling method will be applied to recruit participants from the ambulatory chemotherapy day center of Hong Kong Children's Hospital (HKCH), where a list of all eligible attendees at the center is randomly generated by a computer. The decision to recruit day patients rather than hospitalized patients for the study of the Dreamcatchers Programme is grounded in practical, methodological, and generalizability considerations.

Pediatric oncology patients typically do not remain hospitalized indefinitely. Hospitalizations are often episodic, tied to specific treatment phases (e.g., chemotherapy cycles, management of complications), and vary in duration depending on the individual's condition and progress. In contrast, day patients regularly attend ambulatory chemotherapy day centers for scheduled treatments and are discharged afterwards, providing a more stable recruitment pool. The predictable attendance pattern allows consistent intervention delivery during their visits and facilitates adherence to the intervention schedule (weekly in-person follow-ups) and data collection at baseline (T0), post-intervention (T1), and 3-month follow-up (T2). By recruiting day patients, the study minimizes disruptions caused by fluctuating hospitalization status, ensuring feasibility for this pilot RCT.

Secondly, the Dreamcatchers Programme is designed as a non-pharmacological

intervention intended for use in both hospital and home settings. Recruiting day patients better aligns with the programme's adaptability, allowing the intervention to be tested in the setting where it is most likely to be applied long-term.

Despite hospitalized patients are accessible during their inpatient stay, they face unique environmental constraints (e.g. medical equipment, frequent nursing interruptions) that may limit the applicability of certain intervention components, such as creating a sleep-conducive environment. These hospital-specific barriers could confound results and obscure the intervention's true potential in home settings. Day patients, practicing the intervention at home, provide a more representative sample for evaluating its generalizability, as their sleep environment reflect those experienced by pediatric oncology patients post-treatment or during survivorship.

Furthermore, testing the intervention among day patients ensures that the protocol is feasible for children managing outpatient treatment schedules, enhancing the programme's external validity. By contrast, an inpatient-focused study might yield results less applicable to the broader pediatric oncology population, limiting the programme's scalability.

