### **8.1 Eligibility Criteria**

Principal investigator will approach those who are eligible, inform and ask for consent from caregivers and also assent from children when possible. The purpose of this approach is to avoid selection bias and improve the sample's relevance in the clinical environment.

Participants must meet the following **inclusion criteria**:

- Children who can read and communicate in Chinese
- Aged 6 to 12 years old (school-aged children).
- Diagnosed with cancer and currently undergoing active treatment.
- Identified as experiencing sleep disturbances, defined by a Chinese Pittsburgh Sleep Quality Index (PSQI) global score of  $\geq 5$ .

The following **exclusion criteria** will apply:

- Diagnosed with hematological diseases unrelated to cancer (e.g., sickle cell anemia, thalassemia).
- Presence of severe cognitive impairment, which may hinder the ability to follow instructions or engage with intervention components.

These criteria are designed to select participants who are both clinically relevant and developmentally capable of participating in the intervention and completing required assessments.

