### **10.2 Baseline Assessment (T0)**

At enrollment, all participants will complete the following assessments: demographic survey for data on age, gender, cancer type, and treatment phase, Chinese version of the PSQI for evaluating subjective sleep quality, Chinese PedsQL Cancer Module 3.0 for assessing quality of life, and sleep diary to track sleep patterns and exercise frequency (only for intervention group).

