## Appendix II - Intervention and Data Collection Methods and Procedures

Stage	Description	Assessments/Activities	Participants	Notes
Recruitment and Consent	Recruitment occurs at ambulatory chemotherapy day centers at HKCH. Trained research nurses approach eligible families, provide study details, and obtain informed consent from caregivers and child assent when appropriate.	None	All eligible participants	Consent and assent obtained prior to randomization.
Randomization and Allocation	Participants are randomly assigned to intervention or waitlist control group using concealed block randomization managed by an independent researcher to minimize bias.	None	All participants	Ensures balanced group allocation; performed after consent.
Baseline Assessment (T0)	Conducted at enrollment to establish baseline measures. Assessments include: 
 
Demographic survey (age, gender, cancer type, treatment phase)
 
Chinese PSQI (subjective sleep quality)
 
Chinese PedsQL Cancer Module 3.0 (quality of life)
 
	Demographic survey, Chinese PSQI, Chinese PedsQL Cancer Module v3.0	All participants	Performed after randomization.
Intervention Group: Introductory Session	A total of 60 mins nurse-led group session at education room at HKCH introduces the intervention for up to 10 children and caregivers. includes: 
 
45 mins sleep hygiene education (role of sleep, optimizing sleep environment, addressing poor sleep habits)
 
Demonstration of box-breathing (4-4-4 cycle, 5–10 mins nightly)
 
Demonstration of PMR (tensing/relaxing muscle groups, 10–15 mins nightly)
 
	Sleep diary distribution (intervention group)	Intervention group only	Child-friendly instructions (e.g., “squeeze a lemon” for PMR) ensure engagement.

	
 
• Distribution of sleep diaries with QR code videos for home practice
 
			
Weekly Follow-Ups (Weeks 1–3)	
Weekly in-person sessions at the Integrated Rehabilitation Center reinforce intervention techniques. Nurses:
 
 
• Re-demonstrate box-breathing and PMR
 
• Review sleep diaries to check adherence to nightly practice
 
• Address challenges and clarify techniques
 
	Sleep diary review (intervention group)	Intervention group only	Ensures fidelity and supports adherence. Control group receives general health education to prevent contamination.

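### Eligibility depends on a PSQI score of 5 or more, yet the protocol samples, approaches and randomizes eligible children before any PSQI it describes has been taken

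*Protocol*

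**What the plan says.** Protocol section 8 describes simple random sampling from the ambulatory chemotherapy day centre, "where a list of all eligible attendees at the center is randomly generated by a computer".

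Section 8.1 lists the inclusion criteria. Language, age, and cancer under active treatment can in principle be read from the record or settled on contact. The fourth cannot: "Identified as experiencing sleep disturbances, defined by a Chinese Pittsburgh Sleep Quality Index (PSQI) global score of" 5 or more. The same section says: "Principal investigator will approach those who are eligible, inform and ask for consent from caregivers". Section 10.1 also has staff approach eligible families, and Appendix II repeats it: "Trained research nurses approach eligible families, provide study details, and obtain informed consent from caregivers and child assent when appropriate".

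On timing, section 10.1 moves directly from consent to random assignment. Section 10.2 introduces the first PSQI: "At enrollment, all participants will complete the following assessments". In Appendix II the assessments column is marked as none for both the recruitment row and the randomization row, and the note on the T0 row reads "Performed after randomization".

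On routine care, section 3 says "Patients seldom report their sleep issues thus the problem is rarely being assessed". On outcomes, section 6 has "Feasibility: Measured by recruitment rates, response rates, and retention rates throughout the study".

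**The concern.** The text treats eligibility as known when the list is drawn and when families are approached. One of the four inclusion criteria is a questionnaire score that the protocol does not collect until T0. Section 3 gives no reason to expect a usable score in the medical record.

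Two things are at stake. The first is the integrity of the randomized population: if T0 is the first PSQI and it follows randomization, nothing in the described sequence stops a child scoring below 5 from being randomized. The second is a named feasibility outcome. The pilot is meant to inform larger studies, and the recruitment rate is one of the figures they would use. A rate counted among eligible families leaves out the screening effort, and it needs a PSQI status that is never obtained for families who decline.

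**Working it through.** **The planned size.** Section 8.2 takes 30 per group and 10% attrition. 30 / (1 − 0.10) = 33.3, rounded up to 34 per group, so 2 × 34 = 68. The protocol's figure is reproduced and is not in dispute.

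**The order of steps, as written.**

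| Step | Where | What must be known | Is a PSQI score available? |
|---|---|---|---|
| Random list of eligible attendees | Section 8 | All criteria, including PSQI of 5 or more | No screen described |
| Approach and consent | 8.1, 10.1, Appendix II | Family already eligible | Appendix II: no assessment |
| Randomization | 10.1, Appendix II | Child eligible | Appendix II: no assessment |
| T0, first PSQI | 10.2, Appendix II | – | Yes, but after randomization per Appendix II |

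The first three rows each need information that first appears in the fourth. Section 10.2 alone, which places T0 at enrolment, would allow the PSQI between consent and randomization. Appendix II rules that order out, and section 10.1 names no step between the two.

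**How much screening this could involve (illustration only).** The introduction gives sleep-disturbance prevalences of 13% to 50% in leukemia survivors, about 45% in Hong Kong survivors and up to 80% in children with central nervous system tumours. None is the share scoring 5 or more among children aged 6–12 on active day-centre treatment, so they serve only as assumed values *p*.

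Completed screens needed to find 68 eligible children, if every eligible child joins, are 68 / *p*, rounded up:

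- *p* = 0.80: 85
- *p* = 0.50: 136
- *p* = 0.45: 151.1, so 152
- *p* = 0.13: 523.1, so 524

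**What the denominator does to the rate.** Assume in addition that 70% of approached families consent to screening, whatever the child's score, and that all who qualify are randomized. The 70% is not in the protocol. At *p* = 0.45 the number to approach is 68 / (0.45 × 0.70) = 215.9, so 216.

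- Per family approached: 0.70 × 0.45 = 31.5%. Over *p* = 0.13 to 0.80 this runs from 9.1% to 56%.
- Per eligible child: 70% at every *p*, but not observable, because the score of a child whose family declines is unknown.

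**If no PSQI is checked before randomization.** The expected number of the 68 meeting the criterion is 68 × *p*: about 31 at 45%, 9 at 13% and 54 at 80%. This assumes consenting children are no more likely than others to have poor sleep.

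**The case against.** Several stronger readings are tempting, and the documents do not support them.

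- *The list of eligible attendees could never exist.* Nothing forbids a PSQI screen, and one given before sampling would create the list. The defect is that none is described and that the stated order conflicts with having one. The word eligible in section 8 might also mean eligible on record-based criteria, with the PSQI confirmed at enrolment. That is a sensible design, but Appendix II puts T0 after randomization.
- *The recruitment rate has no valid denominator.* The protocol states no denominator. Families approached, or attendees meeting the record-based criteria, can be counted. A detailed definition may sit in a statistical analysis plan that is not shown, so its absence is no fault here. Only the rate among eligible families is unobservable under the procedure as described.
- *Sites must either give a questionnaire before consent or list children already known to sleep badly.* Consent followed by the PSQI is a third route. Section 3 does not establish that a list of known complaints would be the severe cases: it says when complaints are addressed in routine practice, not when they become known.
- *The treatment comparison is biased.* A source sample that is not random does not by itself bias a 1:1 randomized contrast. The effect is on who is in the trial and on the feasibility figures.

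It is also fair to say that the prevalence inputs are weak and that the range of 85 to 524 is too wide to plan from. They illustrate scale and do not show an error in the 68. What stands is the conflict between an eligibility criterion that needs a PSQI and a sequence that collects none before randomization.

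**Conclusion.** The concern holds as a conflict in stated procedure. Sections 8, 8.1 and 10.1 and Appendix II assume eligibility is known before sampling and approach, while section 10.2 and Appendix II place the first PSQI at enrolment and after randomization respectively. Read together, they do not allow the eligible list to be built, and they leave open the randomization of children scoring below 5. Sampling frame, eligibility check and order of enrolment steps are protocol matters, so this is not detail left to an analysis plan.

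The conflict itself needs no assumption beyond the text. Its numerical size is uncertain: the figure of 85 to 524 screens rests on proxy prevalences drawn mostly from survivors, and the contrast between 31.5% of families approached and 70% of eligible children also rests on an assumed 70% consent to screening. It should be corrected before recruitment starts.

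**What to change.** Reconcile sections 8, 8.1, 10.1 and 10.2 and Appendix II so that they state one sequence:

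1. List the day-centre attendees who meet the record-based criteria (age, cancer under active treatment, Chinese language, no exclusion) and draw the random order from that list.
2. Approach families in that order and obtain parental consent and child assent, covering the screening PSQI.
3. Administer the PSQI before randomization.
4. Randomize only children scoring 5 or more.

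In Appendix II, enter the PSQI before the randomization row and correct the note on the timing of T0. Keep a log, and report the numbers approached, consenting to screening, screened, scoring 5 or more, and randomized. Recruitment can then be given per family approached and at each later step.

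The cost is protocol wording, a sentence in the consent form and a screening log. The sample size stays at 68. The downside is small: some consenting families will screen out, and the reported overall yield will look lower than a rate counted among eligible families.
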